Analytic Plan

Primary Analyses. Our primary research question was if children in the experimental FAM conditions significantly improved their FAM skills from pre-intervention to post-intervention. We did not have a prediction about whether one of the experimental FAM conditions would outperform the other experimental FAM condition. We conducted a repeated-measures ANOVA with timepoint (pre-intervention and post-intervention) as the within-participants factor and condition (size-to-number, mixed, counting, non-numerical) as the between-participants factor, controlling for age, gender, and EF skills. We analyzed planned contrasts for the condition by timepoint interaction that included a complex contrast testing for differences between the experimental (mixed and size-to-number) and control groups (counting and non-numerical) in their FAM task changes across timepoints, as well as simple contrasts comparing FAM changes across timepoints within each of the four conditions. We first examined the FAM mixed trials as our outcome of interest given that children were randomly assigned to complete different versions of the FAM task that varied in if the number or size trials were the pre-switch and post-switch trial levels. This mixed level was the trial level that was the same across all conditions. However, we also ran these analyses using the combined FAM post+mixed accuracy variable as this has been the variable used in prior correlational analyses, and we included FAM version as a covariate.

Exploratory Analyses. To explore potential differences in findings across number and size trials in the FAM task, we repeated our primary analyses, but with the number and size trials and pre- and post-intervention scores as the within-participants factor, controlling for FAM version and other covariates used in prior analyses. We also ran the same repeated-measures ANOVA with three other outcomes (global math achievement, number line estimation, and EF skills) to assess for potential transfer effects.

Results

Descriptive Statistics and Correlations

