predictors of FAM task accuracy. We used the Greenhouse-Geisser correction for sphericity. There was a significant interaction between trial level and version, $F(1.89, 215.49) = 5.49, p = .006, \eta_p^2 = .05$. We explored this interaction by looking at performance across trial levels within each version. We found that scores for children who completed the number first FAM version did not significantly change from pre-switch ($M = .95, SE = .02$) to post-switch trials ($M = .97, SE = .03, t(60) = .94, p = .349$), but they did significantly decrease from both pre-switch trials to mixed trials ($M = .64, SE = .03, t(60) = 10.68, p < .001$) and post-switch trials to mixed trials ($t(60) = 11.49, p < .001$). For the size first FAM version, children's scores significantly decreased from pre-switch ($M = .95, SE = .02$) to post-switch trials ($M = .83, SE = .03, t(54) = 3.08, p = .003$), post-switch trials to mixed trials ($M = .63, SE = .03, t(54) = 5.01, p < .001$), and pre-switch trials to mixed trials ($t(54) = 8.73, p < .001$). We also examined potential differences across versions within each trial level. Within the pre-switch and mixed trial levels, children's scores did not differ by their FAM version condition (all $ps > .05$). Within the post-switch trial level, children scored significantly higher if they completed the number first version compared to the size first version ($t(114) = 3.58, p < .001$).

Primary Analyses

FAM Mixed Trial Level Outcomes. We conducted a 2 (timepoint: pre-intervention and post-intervention) x 4 (condition: counting, mixed, non-numerical, size-to-number) ANOVA predicting children's FAM mixed trial performance as this was the trial level that was identical across all study participants and was predicted to be the level most affected by condition. We also controlled for age, gender, and pretest EF skills. We predicted a significant interaction between timepoint and condition such that children in the experimental conditions (mixed, size-to-number) would significantly improve from pre- to post-intervention in their FAM skills

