compared to control groups (counting, non-numerical). Overall, we did not find a significant interaction effect for timepoint x condition (Wilks' Lambda $F(3, 109) = .96, p = .41, \eta_p^2 = .03$). We then tested our planned comparisons, as they were driven by our hypothesis that FAM ability can be improved through intervention. Prior studies examining the relevance of planned comparisons supported this decision by encouraging researchers to perform planned comparisons regardless of the outcome of the ANOVA analysis, especially when those comparisons are supported by previous findings or theory ([Ruxton & Beauchamp, 2008](#))

First, we examined pre-intervention to post-intervention change in FAM task performance within each condition, and then compared the two experimental conditions to the two control conditions. Children significantly improved their FAM task performance from pre-intervention to post-intervention within the two experimental groups, mixed (Wilks' Lambda $F(1, 109) = 8.65, p = .004, \eta_p^2 = .07$) and size-to-number (Wilks' Lambda $F(1, 109) = 4.77, p = .031, \eta_p^2 = .04$) (See Figure 3). Children did not significantly improve their FAM task performance in the two control group conditions, counting (Wilks' Lambda $F(1, 109) = .54, p = .463, \eta_p^2 = .01$) and non-numerical (Wilks' Lambda $F(1, 109) = 1.77, p = .186, \eta_p^2 = .02$) (See Figure 3). These findings also held when comparing the two experimental conditions to the two control conditions such that children in the two experimental conditions significantly improved their performance (Wilks' Lambda $F(1, 111) = 12.90, p < .001, \eta_p^2 = .10$) (See Figure 4) while children in the control conditions did not (See Figure 2) (Wilks' Lambda $F(1, 111) = 2.11, p = .150, \eta_p^2 = .02$) (See Figure 4).

FAM Post + Mixed Trial Level Outcomes. We also conducted the same analyses with the exception of the outcome variable being the FAM Post+Mixed task performance as this variable has been used in prior FAM studies (Fuhs et al., 2021). We included FAM version as a covariate

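### For FAM mixed trials the planned experimental-versus-control contrast on change is not reported; two within-group tests stand in for it, and the reported omnibus F rules out a contrast significant at two-sided .05

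*Combined protocol and SAP*

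**What the plan says.** The Analytic Plan (Primary Analyses) sets out two kinds of planned contrast for the condition by timepoint interaction. One is between groups: "a complex contrast testing for differences between the experimental (mixed and size-to-number) and control groups (counting and non-numerical) in their FAM task changes across timepoints". The other is within groups: "simple contrasts comparing FAM changes across timepoints within each of the four conditions".

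The Results (Primary Analyses, FAM Mixed Trial Level Outcomes) restate the hypothesis as a comparison: "We predicted a significant interaction between timepoint and condition such that children in the experimental conditions" would improve relative to the two control groups. The interaction is then reported as non-significant, F(3,109) = .96, p = .41, partial eta squared .03. Four within-condition tests follow, and then the sentence at issue: "These findings also held when comparing the two experimental conditions to the two control conditions". The figures attached to it are a within-group test for the pooled experimental conditions (F(1,111) = 12.90, p < .001) and another for the pooled controls, introduced by "while children in the control conditions did not" (F(1,111) = 2.11, p = .150). The text gives no F, p or interval for the difference in change.

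For number line estimation (Potential Transfer Effects) the direct contrast on change is given, F(1,111) = 5.17, p = .025, before the within-group tests.

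**The concern.** The control arms exist so that change under the FAM books can be judged against change under counting books and non-numerical books. Only the between-group contrast does that. A gain that passes .05 in one group and a gain that misses it in another can be nearly equal, particularly when group sizes differ, as they do here (37, 25, 30 and 24).

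The sentence nevertheless tells the reader that the comparison with control came out as predicted. If the omitted contrast is not significant, the comparative prediction on the first-examined outcome is presented as supported when it is not. The direct contrast does appear for an exploratory outcome where it was significant, which makes its absence here more noticeable.

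**Working it through.** **Inputs.** Group sizes are from Power Analysis and Exclusion Criteria: size-to-number 37, mixed 25, counting 30, non-numerical 24, so 62 experimental, 54 control and 116 in all. The F tests are from FAM Mixed Trial Level Outcomes. With three covariates (age, gender, pretest EF) the error df are 116 − 4 − 3 = 109 for four conditions and 116 − 2 − 3 = 111 for two pooled groups, as reported.

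**1. Reproduce the reported figures.** F(3,109) = .96 gives p = .414 and partial eta squared = 2.88 / (2.88 + 109) = .026, matching .41 and .03. The within-group tests also reproduce to rounding; for example, "F(1, 109) = 8.65, p = .004" recomputes to p = .004, and the pooled tests to p = .0005 and .149.

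**2. Upper bound on the missing contrast.** A 1-df contrast inside a 3-df interaction cannot have a larger sum of squares than the interaction.
- Four-condition model: F(1,109) ≤ 3 × .96 = 2.88, so p ≥ .093.
- Collapsed two-group model, with .96 taken as rounded from .965: F(1,111) ≤ 3 × .965 × 111/109 = 2.95, so p ≥ .089.
- Working back from the reported p instead (.41 taken as .405, so omnibus F = .980): F(1,111) ≤ 2.99, p ≥ .086.
- Two-sided .05 critical value: F(1,109) = 3.93. Reaching it would need an omnibus F of at least 3.93 / 3 = 1.31.

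The bound holds for any weighting of the four conditions and needs no assumption about covariate balance.

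**3. Approximate size of the contrast.** Assume a common residual SD of change and ignore covariate imbalance. Each standardised gain is then √(F/n).

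| Group | F | n | Gain (SD of change) |
|---|---|---|---|
| Mixed | 8.65 | 25 | .588 |
| Size-to-number | 4.77 | 37 | .359 |
| Counting | .54 | 30 | .134 |
| Non-numerical | 1.77 | 24 | .272 |
| Experimental, pooled | 12.90 | 62 | .456 |
| Control, pooled | 2.11 | 54 | .198 |

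- From the pooled tests: difference .456 − .198 = .258; SE = √(1/62 + 1/54) = .186; t = 1.39; F = 1.93; p = .17; 95% CI −.11 to .63.
- From the four conditions, equally weighted: (.588 + .359)/2 − (.134 + .272)/2 = .271; SE = ½√(1/25 + 1/37 + 1/30 + 1/24) = .188; t = 1.44; F = 2.06; p = .15; 95% CI −.10 to .64.

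**4. Check on the signs.** An F test does not show direction, so the omnibus F was rebuilt from the table with both experimental gains positive. With both control gains positive it is .98, close to the reported .96. With counting negative it is 2.57, with non-numerical negative 3.38, and with both negative 4.37. Only the all-positive pattern fits, so the controls appear to have gained as well, by less.

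**5. What the labels hide.** Size-to-number is reported as improving and non-numerical as not improving. On the figures above their gains are .359 and .272 SD, a gap of .087 SD.

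**The case against.** - **The primary question is worded within groups.** The Analytic Plan asks whether children in the experimental conditions improved from before to after, and the within-condition tests answer that. This stands as a reason to keep those tests. It does not cover a sentence that claims a comparison, when the same section plans the between-group contrast and the Results predict an interaction.
- **The sentence may mean only that the pattern persisted after pooling.** That reading is possible, and no F or p for superiority is claimed. The wording still says the groups were compared.
- **The null interaction is disclosed, and planned contrasts do not require a significant omnibus test.** Both points are right. The fault is therefore confined to the missing contrast and the inference drawn without it.
- **Sidedness.** No alpha or sidedness is stated for this contrast, and the prediction is directional. At the bound the one-sided p would be about .046 (.044 in the collapsed model with rounding), so the bound alone does not exclude one-sided significance. But no one-sided test is planned, the Results call an interaction p of .070 non-significant, and the reconstruction gives a one-sided p of about .08.
- **The reconstruction is rough.** It is, and its figures illustrate rather than estimate. The bound does not depend on it.
- **The omnibus F could be a misprint.** Other omnibus results are internally inconsistent: post+mixed F(3,105) = .98 implies p = .405, not .591, and number line F(3,109) = 1.82 implies p = .148, not .618. For FAM mixed trials, however, F, p and partial eta squared agree with one another and with the four within-condition tests.
- **Figures are not visible in this copy.** A figure might show the contrast, but it could not make it significant at two-sided .05 against the reported omnibus F.

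**Conclusion.** The concern holds, and the sentence must be corrected. The text omits the planned contrast for FAM mixed trials, and its statement that the findings held in the comparison rests on one significant and one non-significant within-group test. Given the reported omnibus F, the same children and the same covariates, the contrast cannot exceed F of about 2.9 to 3.0 against the 3.93 needed, so p is at least about .09. Its likely value is F of about 1.9 to 2.1, p of about .15 to .17, a difference in gain of roughly 0.26 to 0.27 SD of change with an interval that includes zero. The bound rests on the printed omnibus F, and the conclusion on two-sided .05. The likely value rests also on a common residual SD and negligible covariate imbalance. This does not show that the books have no effect. It shows that a difference from control has not been demonstrated on this outcome.

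**What to change.** In FAM Mixed Trial Level Outcomes, report the already planned contrast by timepoint, (mixed + size-to-number) minus (counting + non-numerical), with its estimate, 95% CI, F and p, and state the alpha and sidedness used. Rest any claim of benefit over control on that result. Keep the planned within-condition tests, described as pre-to-post changes that are not evidence of a difference from control. Replace the sentence at issue with one that follows the contrast; unless the omnibus F proves to be misprinted, it will have to say that a difference from control was not demonstrated at two-sided .05.

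The cost is one contrast from a model already fitted and one reworded sentence, with no new data. The reported result becomes less favourable to the intervention.

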Descriptive statistics are presented in Table 1. Children scored below national norms on both EF skills and math achievement. FAM mixed trial level scores went up from pre-intervention to post-intervention; however, the pre- and post-switch FAM trial level scores went down slightly. We suspect that this occurred because these pre-switch and post-switch accuracy scores were collapsed across the two different FAM forms (size-number and number-size). Given that number and size trials are not necessarily equally difficult for all children, we did not expect FAM accuracy scores to increase on the overall pre- and post-switch levels (Wagner et al., 2023). In the next section, we explored performance across trial levels within each FAM version to further understand the interaction between trial level and FAM version. Correlations are presented in Table 2. As expected, pre-intervention and post-intervention scores for each measure were significantly correlated.

FAM Descriptive Analyses

We first examined if the FAM version children completed affected their performance on the FAM task pre-intervention. We conducted a 3×2 repeated measures ANOVA with FAM trial level (Pre-Switch, Post-Switch, and Mixed) and FAM version (number first or size first) as

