given that children completed either the number or size trials at post-switch. Overall, we did not find a significant interaction effect for timepoint x condition (Wilks' Lambda $F(3, 105) = .98, p = .591, \eta_p^2 = .02$). We then examined our planned contrasts. First, we examined pre-intervention to post-intervention change in FAM task performance within each condition, and then compared the two experimental conditions to the two control conditions. All of these contrasts yielded null findings, suggesting that the intervention changes we observed were due primarily to differences within the FAM mixed trial level rather than the FAM post-switch trial level.

Potential Transfer Effects. We examined pre-intervention to post-intervention changes in overall math achievement, number line estimation, and EF skills. We continued to covary age and gender, and for the math achievement and NLE analyses, we covaried pretest EF skills as a general skill variable. For overall math achievement, we did not find a significant interaction between timepoint and condition (Wilks' Lambda $F(3, 109) = .61, p = .605, \eta_p^2 = .02$), nor did we find significant differences within either experimental or control groups in their pre- to post-intervention FAM score changes. For NLE scores as the outcome variable, we did not find an overall interaction effect between timepoint and condition (Wilks' Lambda $F(3, 109) = 1.82, p = .618, \eta_p^2 = .02$). For planned contrasts, we did not find any significant differences across specific conditions in change from pre-intervention to post-intervention. Combining the two experimental conditions and the two control conditions for the complex contrast, we found a significant difference between the changes in NLE scores of experimental and control groups (Wilks' Lambda $F(1, 111) = 5.17, p = .025, \eta_p^2 = .04$) such that the experimental conditions overall significantly improved their NLE scores from pre- to post-intervention (NLE Pre-Int total = 1.60, SE = .26; NLE T2 total = 2.07, SE = .29; Wilks' Lambda $F(1, 111) = 4.40, p = .038, \eta_p^2 = .04$), while the control conditions did not (NLE Pre-Int total = 2.33, SE = .28; NLE Post-Int total

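### The claim that change lay in the mixed level rather than the post-switch level is untested, and collapsing over two forms does not explain the fall in pre- and post-switch scores

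*Combined protocol and SAP*

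**What the plan says.** The Analytic Plan takes FAM mixed trials as the first outcome and then repeats the analysis on a combined post-switch and mixed score, with FAM version as a covariate.

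- **Mixed trials** (Results, FAM Mixed Trial Level Outcomes). The timepoint by condition interaction is not significant: "Wilks' Lambda $F(3, 109) = .96, p = .41". Within-arm gains are significant in the experimental arms, for example "mixed (Wilks' Lambda $F(1, 109) = 8.65, p = .004" in the mixed-book arm and "Wilks' Lambda $F(1, 111) = 12.90, p < .001" for the two experimental arms together. They are not significant in the controls ("Wilks' Lambda $F(1, 111) = 2.11, p = .150" together).
- **Composite** (Results, FAM Post + Mixed Trial Level Outcomes). The interaction is reported as "Wilks' Lambda $F(3, 105) = .98, p = .591". On the planned contrasts the text says "All of these contrasts yielded null findings", with no statistics. It then concludes that the changes were "due primarily to differences within the FAM mixed trial level rather than the FAM post-switch trial level".
- **Falling scores** (Results, Descriptive Statistics and Correlations). Mixed scores rose, while pre- and post-switch scores fell slightly. The text comments: "We suspect that this occurred because these pre-switch and post-switch accuracy scores were collapsed across the two different FAM forms".

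**The concern.** Saying that change sits in one level rather than another is a claim about a difference between levels. Here it is read from one outcome being significant and another not. The second outcome contains the first, so its null result does not describe post-switch performance.

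The only analysis with trial level as a factor (FAM Descriptive Analyses) uses pre-intervention scores, without condition or timepoint. The exploratory plan crosses number with size trials, not trial levels.

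The primary question is whether FAM skill improved. A null composite and falls on two of the three levels both bear on how general any gain is. The first is accounted for by an untested inference, the second by a mechanism that does not appear to operate.

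**Working it through.** **1. The printed composite result.** F(3, 105) = .98 gives p = .405 and partial η² = 3 × .98 / (3 × .98 + 105) = .027. The text prints p = .591 and .02, which would fit F of about .64. The result is null either way, but the figures need reconciling. The mixed-level figures do reproduce: F(3, 109) = .96 gives p = .414, 8.65 gives .004, 12.90 gives .0005 and 2.11 gives .149.

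**2. What a null composite can show.** Composite change = w × mixed change + (1 − w) × post-switch change. The FAM Skill section gives 12 mixed and 6 post-switch test trials, so w = 12/18 = 2/3 if trials are weighted equally; the weighting is not stated. A test of this sum is not a test of mixed minus post-switch, nor of post-switch alone.

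**3. Within-arm reading.** The sentence most naturally refers to the gains inside the experimental arms, where t = √12.90 = 3.59. Let r be the correlation between changes at the two levels. With equal standard errors, a level difference reaches p < .05 if the post-switch change, in SE units, is below 3.59 − 1.98 × √(2(1 − r)):

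- r = 0: 3.59 − 1.98 × 1.414 = +.79
- r = .3: 3.59 − 1.98 × 1.183 = +1.25

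Post-switch has fewer trials, so its SE may be larger. At 1.3 times the mixed SE, the limits in mixed-SE units are 3.59 − 1.98 × √(1 + 1.69) = +.34 at r = 0, and 3.59 − 1.98 × √(1 + 1.69 − .78) = +.86 at r = .3. No post-switch decline is needed in any of these cases.

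**4. Experimental-versus-control reading.** The Results give two within-group tests for mixed trials but no between-group statistic. It can be rebuilt, assuming a common residual SD and ignoring covariate adjustment of the variances. Change in SD units = √(F/n):

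| Arm | F | n | Change |
|---|---|---|---|
| Mixed | 8.65 | 25 | .588 |
| Size-to-number | 4.77 | 37 | .359 |
| Counting | .54 | 30 | .134 |
| Non-numerical | 1.77 | 24 | .272 |

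- Contrast = (.588 + .359)/2 − (.134 + .272)/2 = .27
- SE = ½ × √(1/25 + 1/37 + 1/30 + 1/24) = .19
- t = 1.44, p about .15

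Check: with all four changes positive, these inputs return an omnibus F of .98 against the printed .96. Negative control changes would give 2.6 to 4.4. Separately, a 1-df contrast in this model cannot exceed 3 × .96 = 2.88, so p is at least .09.

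**5. Pooling over forms.** Power Analysis and Exclusion Criteria gives one split, 61 number-first and 55 size-first. If each child kept one form:

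Pooled change = (61 × change in number-first + 55 × change in size-first) / 116

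This is negative only if at least one form fell. If forms were redrawn at post-test, the mix could shift:

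- Pre-switch: both forms start at .95, so the mix contributes nothing beyond rounding.
- Post-switch: the forms start at .97 and .83, so the shift is .14 × the change in share. Reversing 61/55 to 55/61 gives −.14 × 6/116 = −.007.

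**6. Room to improve.** Pooled pre-intervention accuracy is (61 × .97 + 55 × .83)/116 = .90 at post-switch and (61 × .64 + 55 × .63)/116 = .64 at mixed. Post-switch has about .10 left to gain, mixed about .36.

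**The case against.** The strongest reply is that the localisation is plausible, hedged and partly predicted. The Results say the mixed level was expected to be the most affected, overall mixed scores rose while post-switch scores fell, and the null composite contrasts are disclosed. A rough simulation supports the direction. It took 62 experimental children, an assumed true mixed change of .30 to .46 SD, a post-switch to mixed SD ratio of 1.0 to 1.3, a correlation of 0 to .3 and a mixed weight of 1/2 to 2/3. A significant mixed result with a null composite arose in 6–46% of runs if only mixed changed, against 0–7% if both levels changed equally. This stands: nothing shows the direction to be wrong. It does not replace the missing test.

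Three stronger readings are tempting and not supported:

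- **That localisation would require relative harm at post-switch.** Under equal SEs the between-arm contrast of t = 1.44 would need a post-switch contrast below 1.44 − 2.80 = −1.36 SE at r = 0, or 1.44 − 2.34 = −.90 SE at r = .3. That applies only to the experimental-versus-control comparison. It does not carry over to within-arm gains, where step 3 gives positive limits.
- **That the null composite shows there was no general gain.** Without an interval it is only weak evidence against one.
- **That pooling is impossible as an explanation in every case.** A fixed form per child is implied by the single split and the single version covariate, but not stated outright. The size of the fall is not in the text available, so its importance cannot be judged.

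**Conclusion.** The point holds as a missing test and a faulty explanation. The localisation sentence is untested: it may be right, but the reported analyses cannot show it.

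How easily a test could support it depends on the comparison meant. Within the experimental arms it could succeed without any post-switch decline. That rests on the SE assumption; at r = 0 it holds until the post-switch SE is about 1.5 times the mixed SE (√((3.59/1.98)² − 1) = 1.51). Against control, the mixed-level effect is itself only t = 1.44, p about .15, on the rebuilt contrast.

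The pooling explanation contributes exactly zero to pre-to-post change if form was fixed per child. Without that assumption it still fails for pre-switch, and gives about −.007 for post-switch under a full reversal of the split. A ceiling at post-switch is an unexamined rival explanation for the lack of gain there.

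**What to change.** All of this uses existing data.

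1. Report post-switch change by condition, with confidence intervals.
2. Report the difference in change between the mixed and post-switch levels with intervals and FAM version in the model, both within the experimental arms and as trial level × timepoint × (experimental v control).
3. Report pre-to-post change at each level within each version, and state whether each child kept the same version.
4. State the post-switch ceiling as a competing explanation, and add a sensitivity analysis suited to bounded accuracy, such as a binomial mixed model.
5. Present the localisation as untested or exploratory unless these estimates taken together support it. A single three-way interval with low power should not be the sole rule for keeping or deleting the sentence.
6. Withdraw or reword the pooling explanation, print the composite contrasts, and reconcile p = .591 with F = .98.

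The cost is one or two extra models, some added results and two reworded sentences. The claim will probably be weaker.

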word count on each page was similar across conditions. In the traditional counting, size-to-number, and mixed conditions, the number of objects on each side of the page followed three different simplified ratios: 1:3, 2:3, 1:2. Each page followed these ratios using between 2 and 10 objects on each side of the page, to make sure that the numbers were within the range of numbers which preschool age children are familiar with. The size-to-number and mixed book conditions also varied the total area of objects on each side of each page based on these same three simplified ratios. The ratio of the total area on each side was the inverse of the ratio of total objects on each side. For instance, in a trial where the left side of the page contained 2 objects and the right side contained 4 objects (1:2 ratio), the objects on the left side had a total area that was twice the total area of the objects on the right side (See Figure 2 to view sample pages for each condition). The correct answer was distributed evenly across the right and left sides of pages.

Power Analysis and Exclusion Criteria. A power analysis conducted in G*Power for a 2 (timepoint: pre-intervention and post-intervention) x 4 (condition: counting, mixed, non-numerical, size-to-number) ANOVA, and a within-between interaction, revealed a necessary sample size of 84 participants for the study (21 participants per group). We assumed a medium effect size ($\eta_p^2 = .02$), 2 timepoints, 4 between-participants groups, and a correlation between pre-intervention and post-intervention of $r = .4$ for the power analysis. We initially recruited 169 participants for the study, knowing that school absences during a short-term weeklong study would likely significantly reduce the final sample size. There were 116 participants in the final sample size (Size-to-Number condition $n = 37$, Mixed condition $n = 25$, Counting condition $n = 30$, Non-numerical condition = 24) who were present at all pre-intervention and post-intervention assessments and book reading sessions and had complete assessment data. We randomly

assigned children within each condition to either the number first FAM assessment or the size first FAM assessment (number first n = 61, size first n = 55). Participant exclusions were primarily due to school absences (n = 28), children not wanting to participate in one or more assessments (n = 13), developmental delays (n = 1), and technical errors with the online data collection system (n = 11).

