$= 2.07$, $SE = .21$; Wilks' Lambda $F(1, 111) = 1.37$, $p = .245$, $\eta_p^2 = .01$) (See Figure 5). Finally, we examined condition differences on EF skills changes from pre- to post-intervention. We found a non-significant interaction effect for timepoint x condition (Wilks' Lambda $F(3, 110) = 2.42$, $p = .070$, $\eta_p^2 = .06$). Planned contrasts revealed that only the non-numerical control condition improved their EF skills from pre- to post-intervention (EF Pre-Int = 92.70, $SE = 1.71$; EF Post-Int = 96.38, $SE = 1.95$; Wilks' Lambda $F(1, 110) = 6.32$, $p = .013$, $\eta_p^2 = .05$).

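### Two omnibus results (number line estimation and FAM post+mixed) carry p-values and effect sizes that do not follow from their F statistics, and the printed NLE p and effect size rule out the significant NLE contrast beside them

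*Combined protocol and SAP*

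**What the plan says.** The document reports results as well as methods. Three statements in Results matter here.

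- **NLE omnibus (Potential Transfer Effects).** The timepoint-by-condition interaction is "F(3, 109) = 1.82, p = .618", partial eta-squared .02, described as not significant.
- **NLE contrast (same section).** "Combining the two experimental conditions and the two control conditions for the complex contrast", the authors report a significant difference in change, "F(1, 111) = 5.17, p = .025", partial eta-squared .04. The experimental children improved from 1.60 to 2.07 ("F(1, 111) = 4.40, p = .038"). The control children went from 2.33 to 2.07, with F(1, 111) = 1.37, p = .245.
- **FAM post+mixed omnibus (FAM Post + Mixed Trial Level Outcomes).** The interaction is F(3, 105) = .98, p = .591, partial eta-squared .02. On the model, that section says "We included FAM version as a covariate", and Analytic Plan, Primary Analyses says the same.

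On sample size, Power Analysis and Exclusion Criteria states: "There were 116 participants in the final sample size", all with complete assessment data.

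**The concern.** An F statistic and its two degrees of freedom fix both the p-value and partial eta-squared. In these two lines the three figures do not agree, so at least one in each is wrong.

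The NLE case goes further. The experimental-versus-control contrast is one component of the four-condition comparison. If the whole four-condition effect were as small as p = .618 or partial eta-squared .02 implies, no component of it could be as large as F = 5.17. The printed effect sizes show this directly: .04 for the part and .02 for the whole.

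That contrast is the only significant experimental-versus-control transfer result. As printed, the adjacent omnibus p and effect size exclude it, and anyone reusing the NLE omnibus effect size would take .02 where the F gives .048. For FAM post+mixed, the printed error degrees of freedom also do not match the model the text describes, so a reader cannot be sure which model was fitted.

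**Working it through.** **Formulas.** p is the upper tail of the F distribution. Partial eta-squared = df1·F / (df1·F + df2). With two timepoints, the timepoint-by-condition test is a test on the change score, so error df = N − groups − covariates.

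**1. NLE omnibus, F(3, 109) = 1.82.**
- p = .148 (.147 to .149 over rounding of F). Printed: .618.
- Partial eta-squared = 5.46 / (5.46 + 109) = .048. Printed: .02.
- p = .618 needs F = .60. A partial eta-squared that rounds to .02 (.015 to .025) needs F between .55 and .93.

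**2. FAM post+mixed omnibus, F(3, 105) = .98.**
- p = .405 (.403 to .408 over rounding). Printed: .591.
- Partial eta-squared = 2.94 / (2.94 + 105) = .027. Printed: .02.
- p = .591 needs F = .64, which gives partial eta-squared .018. The printed p and effect size therefore agree with each other but not with F.
- With 108 error df, p is still .405 and partial eta-squared .027.

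No error df from 105 to 114 and no numerator df from 1 to 4 gives either printed p.

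**3. Comparison with the rest of Results.** The same check on the other 14 F results printed with p and partial eta-squared shows agreement to rounding or within about .005. The largest gap in p is for math achievement, .605 printed against .610. The two lines above miss by .47 and .19.

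**4. NLE omnibus against the NLE contrast.** The error df support the same 116 children and three covariates (age, gender, pretest EF) in both models: 116 − 4 − 3 = 109 for four conditions and 116 − 2 − 3 = 111 for two pooled groups. The two-group model is nested in the four-condition model, so the omnibus partial eta-squared cannot be below the contrast's. In terms of F:

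contrast F ≤ 3 · F(omnibus) · 111/109

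| Omnibus figure taken as true | Omnibus F | Largest possible contrast F | p of that contrast |
|---|---|---|---|
| p = .618 | .597 | 1.83 | .18 |
| partial eta-squared at most .025 | .932 | 2.85 | .094 |
| F = 1.82 | 1.82 | 5.56 | – |

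The printed contrast is 5.17. In reverse, it needs an omnibus F of at least 5.17 × 109 / (3 × 111) = 1.69, so p of at most .173. Only the printed F = 1.82 meets that. If the contrast had instead come from the four-condition model, the bound would be similar: F at least 5.17 / 3 = 1.72, p at most .166.

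**5. Is the contrast itself plausible?** F(1, 111) = 5.17 gives p = .025 and partial eta-squared .0445, as printed. From the within-group results:
- Changes: 2.07 − 1.60 = +.47 and 2.07 − 2.33 = −.26.
- Standard errors: .47/√4.40 = .224 and .26/√1.37 = .222.
- Contrast F ≈ .73² / (.224² + .222²) = 5.35, or 5.25 to 5.45 over rounding.

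This treats the two adjusted changes as independent. The printed 5.17 lies just below the range; a correlation of about −.035 between the adjusted changes closes the gap. Either way the value is far above both caps.

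**6. Error df for FAM post+mixed.** Age, gender, EF and FAM version as four covariates leave 116 − 4 − 4 = 108. The printed 105 would arise if version were a factor crossed with condition: 116 − 8 − 3 = 105.

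**The case against.** The mismatches themselves cannot be argued away, but their weight can. NLE is an exploratory outcome, and post+mixed was run in addition to the mixed-trial outcome. Both omnibus tests are non-significant whichever figure is right, and the authors state that planned comparisons go ahead regardless of the omnibus. The effect size attached to the transfer claim is the contrast's own .04, which is correct for its F. All of this stands, and it is why the point is a reporting correction and not a challenge to the primary result.

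It can also be said that the NLE contrast is self-consistent and supported by its within-group results, so nothing impugns it except an omnibus p and effect size that are probably misprinted. That is fair. The evidence favours F = 1.82 and the contrast. It remains an inference from printed figures, however, and since the omnibus line must be checked anyway, reproducing the contrast from the same run adds almost nothing.

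Two further cautions hold. No source output is visible, so the cause of the post+mixed error is unknown. Wilks' Lambda for p = .591 is 1 − .018 = .982, so Lambda may have been printed as F, but that is only a lead to check. Likewise, a crossed factor is not the only way to reach 105. It could be a misprint, or 113 children (113 − 4 − 4 = 105), although the latter conflicts with the statement that all 116 had complete data.

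**Conclusion.** The concern holds. Two reported omnibus results are wrong as printed.

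- **NLE:** p is .148 for the printed F, not .618, and partial eta-squared is .048, not .02, a factor of 2.4. The p and effect size are the likelier errors, because only F = 1.82 is compatible with the contrast of 5.17. This rests on the same children and covariates in both NLE models, which the error df support.
- **FAM post+mixed:** p is .405 for the printed F, not .591, and partial eta-squared is .027, not .02. Here p and effect size agree with each other at F = .64, so F may be the wrong entry; the document does not settle it. Separately, 105 error df does not match a model with FAM version as a single covariate (108). That discrepancy does not explain the p mismatch.

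No significance decision changes, and the FAM mixed-trial result is unaffected.

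**What to change.** - Check both omnibus models against the source output, or re-run them on the 116-child file, and print F, df, p and partial eta-squared from one run.
- If NLE F = 1.82 is confirmed, print p = .148 and partial eta-squared .048. Confirm the experimental-versus-control contrast in the same run and retain the claim if it reproduces.
- If post+mixed p = .591 is confirmed, print F = .64 and check whether .98 is Wilks' Lambda. If F = .98 is confirmed, print p = .405 and partial eta-squared .03.
- Explain the 105 error df. State whether FAM version was a covariate or a factor crossed with condition, and the number analysed, so that text and df agree in both the Analytic Plan and Results.

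The cost is a check of two model outputs, or two re-runs, and corrected text. No new data are needed.
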